67 PRIVILEGED AND CONFIDENTIAL COMMUNICATION

705
Protocol
$\mathcal{O}$
Ř
 
ar
Ĩ.
щ
is
S
a
ä
$\triangleleft$
Ξ
8
Ξ·
N.
E
t,

	Overall Incidence (N=X)																						
jections	Overall (N=X)																						
vt DNA, 4 in X)	Admin 3 (N=X)																						
8 mg ZIKVv (N=)	Admin 2 (N=X)																						
Group 3:	Admin 1 (N=X)																						
ections	Overall (N=X)																						
vt DNA, 4 inj X)	Admin 3 (N=X)																						
: 4 mg ZIKV v (N=)	Admin 2 (N=X)																						
Group 2	Admin 1 (N=X)																						
ijections	Overall (N=X)																						
wt DNA, 2 in =X)	Admin 3 (N=X)																						
l: 4 mg ZIKV (N =	Admin 2 (N=X)																						
Group ]	Admin 1 (N=X)																						
	Symptoms Intensity	Missing	CHILLS	None	Mild	Moderate	Severe	Missing	NAUSEA	None	Mild	Moderate	Severe	Missing	JOINT PAIN	None	Mild	Moderate	Severe	Missing	TEMPERATURE	None	Mild

68 PRIVILEGED AND CONFIDENTIAL COMMUNICATION

	Overall Incidence (N=X)										
ections	Overall (N=X)										
vt DNA, 4 inj X)	Admin 3 (N=X)										
8 mg ZIKVv (N=)	Admin 2 (N=X)										
Group 3:	Admin 1 (N=X)										
ections	Overall (N=X)										
wt DNA, 4 inj X)	Admin 3 (N=X)										
: 4 mg ZIKV (N=	Admin 2 (N=X)										
Group 2	Admin 1 (N=X)										. :
ijections	Overall (N=X)										or each subject
 wt DNA, 2 ir =X)	Admin 3 (N=X)										post dosing fc
l: 4 mg ZJKV (N	Admin 2 (N=X)										erity reported
Group	Admin 1 (N=X)										maximum sev
	Symptoms Intensity	Moderate	Severe	Missing	ANY SYSTEMIC SYMPTOM	None	Mild	Moderate	Severe	Missing	Severity is the

Table with similar format:

41
$\circ$
—
0
S
0
Ĕ
2
5
()
$\tilde{\mathbf{x}}$
μ 
>
ŕ.
- 
ц
а
7
щ
70
/SIS
lysi
alysis
nalysis
Analysis
Analysis
al Analysis
cal Analysis
ical Analysis
stical Analysis
istical Analysis
atistical Analysis
tatistical Analysis
Statistical Analysis

- Number and Percentage of Subjects Experiencing Solicited Events by Symptom, Maximum Severity, Administration, and Study Group, Safety Analysis Population – Part B Table 63:
- by MedDRA® System Organ Class and Preferred Term, and Study Group, Safety Analysis Population Post Any Number and Percentage of Subjects Experiencing Unsolicited Adverse Events with 95% Confidence Intervals Administration-Part A Table 64:

	Group	1: 4 mg Zl	lKVwt DNA, 2	Group 2	:: 4 mg Z	JIKVwt DNA, 4	Group 3	3: 8 mg ZI	KVwt DNA, 4			
		injecti (N=7	ions X)		inject (N=	ions X)		injecti (N=N	ons ()		Fisher's Exact p-value	
SYSTEM ORGAN CLASS/ Preferred Term	u	%	95% CI	u	%	95% CI	u	%	95% CI	Group 1 vs Group 2	Group 2 vs Group 3	Group 1 vs Group 3
SYSTEM ORGAN CLASS #1	х	х	X.X-X.X	х	Х	Х.Х-Х.Х	х	х	X.X-X.X	X.XXX	X.XX	X.XXX
Preferred Term #1	х	х	Х.Х-Х.Х	х	х	Х.Х-Х.Х	х	x	Х.Х-Х.Х	X.XXX	X.XX	X.XXX
Preferred Term #2	х	х	X.X-X.X	х	Х	Х.Х-Х.Х	х	х	X.X-X.X	X.XXX	X.XX	X.XXX
SYSTEM ORGAN CLASS #2	Х	х	Х.Х-Х.Х	х	х	Х.Х-Х.Х	х	х	Х.Х-Х.Х	X.XXX	X.XXX	X.XXX
Preferred Term #1	х	х	X.X-X.X	х	Х	Х.Х-Х.Х	х	х	X.X-X.X	X.XXX	X.XX	X.XXX
Preferred Term #2	x	х	X.X-X.X	х	х	Х.Х-Х.Х	х	x	Х.Х-Х.Х	X.XXX	X.XX	X.XX
SYSTEM ORGAN CLASS #3	Х	х	X.X-X.X	х	х	Х.Х-Х.Х	х	х	Х.Х-Х.Х	X.XXX	X.XX	X.XX
Preferred Term #1	x	х	Х.Х-Х.Х	х	х	Х.Х-Х.Х	х	х	Х.Х-Х.Х	X.XXX	X.XXX	X.XXX
Preferred Term #2	x	х	Х.Х-Х.Х	х	х	Х.Х-Х.Х	х	х	Х.Х-Х.Х	X.XXX	X.XXX	X.XXX
Note: A subject is counted at most or	nce per SC	DC and PT	- - -	:	-							

N = the number of subjects in the Safety analysis population who received the applicable dose.

[Implementation note: Table for Part A should use Fisher's exact test for calculating p-values. Tables for Part B should use Chi-square test for calculating p-values.]

## Number and Percentage of Subjects Experiencing Unsolicited Adverse Events with 95% Confidence Intervals by MedDRA® System Organ Class and Preferred Term, and Study Group, Safety Analysis Population Post First Administration– Part A Table 65:

[Implementation note: Table will only include unsolicited adverse events occurring after the first administration but before the second 1 .......

autilitistiauoli. J													
	ModDDA @ Professor	P Gre ZIK i	ost Do oup 1: Vwt I njectic (N=X	se 1 4 mg NA, 2 0ns	ZII C	Post D roup 2 KVwt inject (N=	ose 1 :: 4 mg DNA, 4 ions X)	P Group 3 DNA	ost Dose i: 8 mg Z , 4 inject (N=X)	1 JKVwt ions		All Subj (N=X	ects
MedDRA® System Organ Class	Term	u	%	95% CI	u	%	95% CI	u	%	95% CI	u	%	95% CI
Any SOC	Any PT	x	х.х	х.х, х.х	х	X.X	х.х, х.х	х	х.х	х.х, х.х	x	х.х	х.х, х.х
[SOC 1]	Any PT												
	[PT 1]												
	[PT 2]												
[SOC 2]	Any PT												
	[PT 1]												
	[PT 2]												

Note: This table presents number and percentage of subjects. A subject is only counted once per PT/time point.

705
Protocol
C
KR
1
Plan
/SIS
-
Ana
al
atistic
ت

- Number and Percentage of Subjects Experiencing Unsolicited Adverse Events with 95% Confidence Intervals by MedDRA® System Organ Class and Preferred Term, and Study Group, Safety Analysis Population Post Second Administration– Part A Table 66:
- Number and Percentage of Subjects Experiencing Unsolicited Adverse Events with 95% Confidence Intervals by MedDRA® System Organ Class and Preferred Term, and Study Group, Safety Analysis Population Post **Third Administration– Part A** Table 67:
- oy MedDRA® System Organ Class and Preferred Term, and Study Group, Safety Analysis Population Post Any Number and Percentage of Subjects Experiencing Unsolicited Adverse Events with 95% Confidence Intervals Administration-Part B Table 68:
- Number and Percentage of Subjects Experiencing Unsolicited Adverse Events with 95% Confidence Intervals by MedDRA® System Organ Class and Preferred Term, and Study Group, Safety Analysis Population Post First Administration– Part B Table 69:
- Number and Percentage of Subjects Experiencing Unsolicited Adverse Events with 95% Confidence Intervals by MedDRA® System Organ Class and Preferred Term, and Study Group, Safety Analysis Population Post Second Administration– Part B Table 70:
- Number and Percentage of Subjects Experiencing Unsolicited Adverse Events with 95% Confidence Intervals by MedDRA® System Organ Class and Preferred Term, and Study Group, Safety Analysis Population Post **Third Administration– Part B** Table 71:
- Number and Percentage of Subjects Experiencing Unsolicited Adverse Events with 95% Confidence Intervals by MedDRA® System Organ Class and Preferred Term, All Enrolled Subjects, Pre-First Administration Table 72:
- Organ Class and Preferred Term, Severity, Relationship, and Study Group Part A, Group 1 (N=X) Number and Percentage of Subjects Experiencing Unsolicited Adverse Events by MedDRA® System Table 73:

						Sever	ity			Rel	ationship 1	to Treatme	nt
		Any Inc	sidence	Mil	þ	Моdел	ate	Seve	re	Not Re	lated	Rela	ted
MedDRA® System Organ Class	MedDRA® Preferred Term	u	%	u	%	u	%	u	%	u	%	u	%
Any SOC								x					
	Any PT	х	х.х	x	х.х	x	х.х		x.x	x	х.х	х	х.х
[SOC 1]													
	Any PT												
	[PT 1]												
	[PT 2]												
[SOC 2]	Any PT												
	[PT 1]												
	[PT 2]												

Note: This table presents number and percentage of subjects. A subject is only counted once per PT and is summarized according to their highest severity and closest relationship.

Tables with similar format:

- Organ Class and Preferred Term, Severity, Relationship, and Study Group Part A, Group 2 (N=X) Number and Percentage of Subjects Experiencing Unsolicited Adverse Events by MedDRA® System Table 74:
- Organ Class and Preferred Term, Severity, Relationship, and Study Group Part A, Group 3 (N=X) Number and Percentage of Subjects Experiencing Unsolicited Adverse Events by MedDRA® System Table 75:

705
Protocol
$\mathcal{O}$
Ř
1
Plan
ysis
Anal
cal 7
tistic
Stal

Organ Class	and Preferred Term, So	everity,	Relatic	onshij	o, and	Stud	y Gre	– dno	Part ]	B, Grou	ıp 4 (N=	X )	
						Seve	rity			Re	lationship	to Treatme	ent
		Any Inc	sidence	Mi	p	Mode	rate	Sev	ere	Not R	elated	Rela	ited
MedDRA® System Organ Class	MedDRA® Preferred Term	u	%	u	%	u	%	u	%	u	%	u	%
Any SOC	Any PT	х	х.х	x	х.х	×	х.х	x	х.х	x	х.х	x	х.х
[SOC 1]	Any PT												
	[PT 1]												
	[PT 2]												
[SOC 2]	Any PT												

Number and Percentage of Subjects Experiencing Unsolicited Adverse Events by MedDRA® System Table 76:

Tables with similar format:

[PT 1] [PT 2]

- Organ Class and Preferred Term, Severity, Relationship, and Study Group Part B, Group 5 (N=X) Number and Percentage of Subjects Experiencing Unsolicited Adverse Events by MedDRA® System Table 77:
- Organ Class and Preferred Term, Severity, Relationship, and Study Group Screening Segment (N=X) Number and Percentage of Subjects Experiencing Unsolicited Adverse Events by MedDRA® System Table 78:

#### Number and Percentage of Subjects Experiencing Related Unsolicited Adverse Events by MedDRA® System Organ Class and Preferred Term, Severity, and Study Group – Part A, Group 1 (N=X) Table 79:

	-				-				
	/ere	%	х.х						
	Sev	u	х						
rity	erate	‰	х.х						
Seve	Mod	u	х						
	ild	%	х.х						
	Μ	u	х						
	cidence	%	хх						
	Any In	u	х						
		MedDRA® Preferred Term	Any PT	Any PT	[PT 1]	[PT 2]	Any PT	[PT 1]	[PT 2]
		MedDRA® System Organ Class	Any SOC	[SOC 1]			[SOC 2]		

Note: This table presents number and percentage of subjects. A subject is only counted once per PT and is summarized according to their highest severity.

Tables with a similar format:

- Number and Percentage of Subjects Experiencing Related Unsolicited Adverse Events by MedDRA® System Organ Class and Preferred Term, Severity, and Study Group – Part A, Group 2 (N=X) Table 80:
- Number and Percentage of Subjects Experiencing Related Unsolicited Adverse Events by MedDRA® System Organ Class and Preferred Term, Severity, and Study Group – Part A, Group 3 (N=X) Table 81:

Number and Percentage of Subjects Experiencing Related Unsolicited Adverse Events by MedDRA®	System Organ Class and Preferred Term, Severity, and Study Group – Part B, Group 4 (N=X)
Fable 82:	

						Seve	rity		
		Any In	cidence	Μ	ild	Mode	erate	Sev	ere
MedDRA® System Organ Class	MedDRA® Preferred Term	u	%	u	%	u	⁰‰	u	%
Any SOC	Any PT	х	х.х	х	х.х	х	х.х	х	х.х
[SOC 1]	Any PT								
	[PT 1]								
	[PT 2]								
[SOC 2]	Any PT								
	[PT 1]								
	[PT 2]								

Note: This table presents number and percentage of subjects. A subject is only counted once per PT and is summarized according to their highest sevenity

Tables with similar format:

- Number and Percentage of Subjects Experiencing Related Unsolicited Adverse Events by MedDRA® System Organ Class and Preferred Term, Severity, and Study Group – Part B, Group 5 (N=X) Table 83:
- Number and Percentage of Subjects Experiencing Related Unsolicited Adverse Events by MedDRA® System Organ Class and Preferred Term, Severity, and Study Group Screening Segment (N=X) Table 84:

		Post 1 (N=	ose 1 ⊧X)	Post I (N=	lose 2 ±X)	Post I (N=	)ose 3 ⊧X)	Post Ar (N=	y Dose X)
MedDRA® System Organ Class	MedDRA® Preferred Term	u	%	u	%	u	%	u	%
Any SOC	Any PT	x	х.х	x	х.х	х	х.х	x	х.х
[SOC 1]	Any PT								
	[PT 1]								
	[PT 2]								
[SOC 2]	Any PT								
	[PT 1]								
	[PT 2]								

Note: This table presents number and percentage of subjects. A subject is only counted once per PT/Time point.

Tables with similar format:

- Number and Percentage of Subjects Experiencing Related Unsolicited Adverse Events Post Dosing by MedDRA® System Organ Class and Preferred Term, Dose, and Study Group – Part A, Group 2 Table 86:
- Number and Percentage of Subjects Experiencing Related Unsolicited Adverse Events Post Dosing by MedDRA® System Organ Class and Preferred Term, Dose, and Study Group Part A, Group 3 Table 87:

Number and Percentage of Subjects Experiencing Related Unsolicited Adverse Events Post Dosing by MedDRA® System Organ Class and Preferred Term, Dose, and Study Group – Part B, Group 5 Table 89:

Number of Unsolicited Adverse Events by MedDRA® System Organ Class and Preferred Term, Dose, and Study Group – Part A, Group 1 Table 90:

[Implementation Note: Day x-y interval should correspond to period of collection for solicited symptoms, if applicable. Day y-z interval should be up until subsequent dose.]

		Post Dose 1	Post Dose 2	Post Dose 3	Post Any Dose	
MedDRA® System Organ Class	MedDRA® Preferred Term	# of Events	# of Events	# of Events	# of Events	
Any SOC	Any PT	х	x	x	х	
[SOC 1]	Any PT					
	[PT 1]					
	[PT 2]					
[SOC 2]	Any PT					
	[PT 1]					
	[PT 2]					

Note: This table presents number of events.

Table with similar format:

Ś
0
$\sim$
1
8
ŏ
ž.
2
Ā
$\overline{r}$
Ų.
2
$\geq$
` .
÷
H
Ë.
Ъ
S C
SIS
ysis
alysis
nalysis
Analysis
Analysis
al Analysis
cal Analysis
tical Analysis
istical Analysis
ttistical Analysis
tatistical Analysis

- Number of Unsolicited Adverse Events by MedDRA® System Organ Class and Preferred Term, Dose, and Study Group – Part A, Group 2 Table 91:
- Number of Unsolicited Adverse Events by MedDRA® System Organ Class and Preferred Term, Dose, and Study Group – Part A, Group 3 Table 92:
- Number of Unsolicited Adverse Events by MedDRA® System Organ Class and Preferred Term, Dose, and Study Group – Part B, Group 4 Table 93:
- Number of Unsolicited Adverse Events by MedDRA® System Organ Class and Preferred Term, Dose, and Study Group – Part B, Group 5 Table 94:

Ľ,
$\approx$
`
0
õ
0
Ħ
ŭ
D,
$\tau$
Ų.
2
$\geq$
۲.
 
Ξ
10
Р
70
S.
Ę,
g
9
$\triangleleft$
_
g
. 2
5
· #
at
Ľ,
· •

Number and Percentage of Subjects Experiencing Adverse Events Above 5% Frequency Threshold by MedDRA System Organ Class, Preferred Term, and Study Group – Part A Table 95:

	Gro	up 1:	Grou	p 2: 4	Grou	p 3: 8
	4	ng	Ξ	ы Б	n	ğ
	ZIK	Vwt	ZIK	Vwt	ZIK	Vwt
	NQ	A, 2	DN	A , 4	DN	A, 4
	injec	tions	injec	tions	injec	tions
	Ż	=X)	Ľ,	=X )	Ż	=X)
	u	%	u	‰	u	%
At least one solicited or unsolicited						
adverse event above 5%						
[SOC 1]						
[PT 1]						
[PT 2]						
[SOC 1]						

Table with similar format:

Number and Percentage of Subjects Experiencing Adverse Events Above 5% Frequency Threshold by MedDRA System Organ Class, Preferred Term, and Study Group – Part B Table 96:

Protocol 705
$\overline{\mathbf{O}}$
VR(
́т.
lan
Ы
vsis
vnal.
<,
al
Statistic

#### Table 97:Overall Summary of Adverse Events

	Grou Grou DN/ DN/ inject	o 1:4 KVwt A, 2 ions X)	Group BNA DNA injecti (N=)	2: 4 2 Wut , 4 ons	Grou 8 n DNA DNA inject	p 3: ng Vwt X) 4 X)	[Grot 4] (N=X	£	[Grou] 5] (N=X	b A A	l Part A ubjects (N=X)	All N.	Part B bjects √=X)	All Random Subjec (N=X	uized cts ()	Subjects in Screening	r
Subjects a with	u	%	, u	%	п	%	, u	%	ц ц	~ 1	, I	, n	%	u	%	u	T
																	1
At least one local solicited reactogenicity	Х	х	x	х	х	х	х	x	x	x	x	x	х	x	х	ı	1
At least one systemic solicited reactogenicity	Х	х	x	х	x	x	x	x	x	x x	x	х	х	x	х		1
At least one unsolicited adverse event	х	х	x	x	x	x	x	×	×	×	x	x	x	x	х	x	
At least one related unsolicited adverse event	Х	х	x	х	x	x	x	x	x	x	x	х	х	x	х	x	
Mild (Grade 1)	x	×	x	х	x	х	x	x	×	×	x	х	x	x	х	x	
Moderate (Grade 2)	x	×	x	х	x	x	x	x	x	×	x	x	x	x	х	x	
Severe (Grade 3)	х	х	x	х	x	х	x	x	×	×	x	х	x	x	х	х	
Not yet assessed																	
At least one severe (Grade 3) unsolicited adverse event	x	x	x	x	×	×	×	x	×	×	×	×	x	x	x	x	
Related	х	х	x	x	x	x	x	×	×	×	x	x	x	x	х	x	
Unrelated	х	х	х	X	х	x	х	х	х	x x	x	х	x	x	х	Х	
At least one serious adverse event b	х	х	х	х	х	х	х	х	x	x x	x X	х	x	x	х	х	
At least one related, serious adverse event	х	х	х	х	х	х	х	х	х	x 2	x	х	х	х	х	х	
At least one adverse event leading to early termination c	х	Х	x	x	×	x	×	x	×	x x	x	x	х	x	х	х	
At least one new onset chronic medical condition	х	х	x	х	x	х	x	x	x	x x	x	x	x	x	х		

Statistical Analysis Plan - VRC Protocol 705

	Grou mg Zl DN iniec	p 1: 4 KVwt A, 2	Group mg ZIH DNA iniect	2: 4 «Vwt ., 4	Grou 8 n ZIK DNA	p 3: ng Vwt ions	[Grou	đ	[Group		Part A Diects	All Pa	urt B ects	All Random Subiec	ized	Subiects in
	-N)	=X)	(N=)	X)	=N)	X)	K=N)	()	(X=N)	n U	=X)		X)	X=N)	er (	Screening
Subjects a with	u	%	n	%	n	%	n	%	n %	n	%	n	%	n	%	n
N = Number of subjects in the Safety Population	u															
a Subjects are counted once for each category re	gardless	of the nu	mber of e	vents.												
b A listing of Serious Adverse Events is included	d in Tab	e 99 thro	ugh Table	\$ 101.												
c As reported on the Adverse Event eCRF.																

## Number and Percentage of Subjects Experiencing Serious Adverse Events by MedDRA System Organ Class, Preferred Term, and Study Group Table 98:

			ı										
SVSTEM ORGAN CLASS	Group ZIKVwt injec (N=	1: 4 mg : DNA, 2 tions =X)	Group 2 ZIKVw1 4 injec (N=)	:: 4 mg t DNA, tions X)	Group ZIKVwt injec (N=	3: 8 mg : DNA, 4 tions ≞X)	[Gro (N=	лр 4] (X)	[Grou (N=)	up 5] X)	All Ran Sub l (N=	do mized jects =X)	Subjects in Screening
Preferred Term	u	%	u	%	u	%	u	%	u	%	u	%	u
SYSTEM ORGAN CLASS #1	x	x	х	x	x	x	x	x	х	x	x	х	x
Preferred Term #1	x	x	х	x	x	x	x	x	х	x	x	x	x
Preferred Term #2	x	х	x	x	х	х	x	х	х	х	х	х	х
SYSTEM ORGAN CLASS #2	x	х	Х	x	х	x	х	х	х	х	х	х	х
Preferred Term #1	x	х	х	x	х	х	x	х	х	х	х	х	х
Preferred Term #2	x	х	x	x	х	х	x	х	х	х	x	х	х
SYSTEM ORGAN CLASS #3	x	х	х	x	x	x	x	x	х	x	x	x	х
Preferred Term #1	x	х	Х	x	х	x	х	х	х	х	х	х	х
Preferred Term #2	x	х	x	х	x	x	х	х	x	х	x	х	х
Note: A subject is counted at most $c = N = the number of subjects in the S2$	once per SO	C and PT is nomilatio	5										

82 PRIVILEGED AND CONFIDENTIAL COMMUNICATION

### Table 99:Listing of Serious Adverse Events – Part A

#1										
Subject ID	Study Group	AE Number	Adverse Event	Associated with Dose #	# of Days Associated	Post Dose	Duration (Days)	Reason Reported as an SAE	Severity	
#2										1
Subject ID	Adverse Event	Relationship to Study Treatment	Action Taken with Study Treatment	Subject Discontinued Due to AE	Outcome		Comments			

### Table 100: Listing of Serious Adverse Events – Part B

# 1

Severity				
Reason Reported as an SAE			Comments	
Duration (Days)				
# of Days Post Associated Dose			Outcome	
Associated with Dose #			Subject Discontinued Due to AE	
dverse Event			Action Taken with Study Treatment	
er A			lationship o Study reatment	
AE Numb			Re t T	
Study Group			Adverse Event	
Subject ID		# 2	Subject ID	

RC Protocol 705
5
- I
Plan
Analysis
tatistical 

# Table 101: Listing of Serious Adverse Events – Screening Segment

Comments	
Outcome	
Action Taken with Study Treatment	
Severity	
Reason Reported as an SAE	
Duration (Days)	
Adverse Event	
AE Number	
Study Group	
Subject ID	

# Table 102: Listing of Non-Serious, Unsolicited, Moderate or Severe Adverse Events – Part A

# 1						- -			
Subject ID	Study Group	AE Number	Adverse Event	Associated with Dose #	# of Days Associated	s Post d Dose	Duration (Days)	Severity	
									r
#2									1
Subject ID	Adven Ever	rse Relationshif rse to Study tt Treatment	o Action Taken with Study Treatment	Subject Discontinued Due to AE	Outcome		Comments		

#### - Part R Table 103: – Listing of Non-Serious, Unsolicited, Moderate or Severe Adverse Events -

			]		
	Severity				
	Reason Reported as an SAE				
us – Fait d	Duration (Days)			Comments	
rse Even	ays Post ited Dose				
ere Auve	# of D Associa			Outcome	
louerate of Dev	Associated with Dose #			Subject Discontinued Due to AE	
	Adverse Event			Action Taken with Study Treatment	
voll-Serious, v	Number /			Relationship to Study Treatment	
	ly AF			Adverse Event	
	Stud Grou			4	
# 1	Subject ID		#2	Subject ID	

# Table 104: Listing of New Onset Chronic Medical Conditions – Part A

Treatment		
Severity		
(Days)		
Date		
Dose		
Dose #		
Date		
Event		
Number		
Group		
(Years)		
Ð		
	ID (Years) Group Number Event Date Dose Date (Days) Severity Treatment	ID (Years) Group Number Event Date Dose Date (Days) Severity Treatment

Table with similar format:

Table 105:Listing of New Onset Chronic Medical Conditions – Part B

Narratives of Deaths, Other Serious and Significant Adverse Events- All Enrolled Subjects Table 106:

Groun 4 vs Groun 5	p-value	X.XXX		X.XX		X.XXX
	95% CI	х.х, х.х		X.X, X.X		X.X, X.X
Overa (N=X)	%	х.х		х.х		х.х
	u	x		х		Х
و 5] د)	95% CI	х.х, х.х	ı Negative	X.X, X.X	a Positive	X.X, X.X
[Grou] (N=)	%	х.х	line Zika	х.х	sline Zik	X.X
	u	x	Base	х	Base	х
up 4] X)	13 %Se	х.х, х.х		х.х, х.х		X.X, X.X
[Grou (N=	%	x.x		х.х		х.х
	u	×		х		х
		Confirmed DENV Case		Confirmed DENV Case		Confirmed DENV Case

## Table 107: Confirmed Cases of DENV, Safety Population – Part B

#### Number of Pregnancies by Outcome and Study Group – Part A Table 108:

	Group 1: 4 mg ZIKVwt DNA, 2 injections (N=X)	Group 2: 4 mg ZJKVwt DNA, 4 injections (N=X)	Group 3: 8 mg ZJKVwt DNA, 4 injections (N=X)	All Subjects (N=X)
Total pregnancies	x	x	x	x
Live birth	X	Х	х	х
Congenital anomalies	x	X	х	х
Neonatal deaths	x	X	х	х
Miscarriage	х	х	х	х
Elective abortion	х	х	х	х
Ectopic pregnancy	x	X	х	х
Still birth	Х	Х	х	х
Congenital anomalies	Х	Х	Х	Х

Table with similar format:

Table 109: Number of Pregnancies by Outcome and Study Group – Part B

Distribution of Laboratory Results (Binary-Graded) by Parameter, Severity, Study Day, and Study Group – Part A Table 110:

[For binary parameters, not contained in tox table]

		Grou	p 1: 4 i	mg ZIK injectio	(Vwt ] ns	DNA, 2	Grou	up 2: 4	mg ZIK injectioi	(Vwt ] 1S	DNA, 4	Grou	ıp 3: 8 4 i	mg ZII njectio	KVwt I ns	DNA,
		Ζ	Nor	mal.	Abn	ormal	Ζ	No	rmal	Abn	ormal	Ζ	Nor	mal	Abno	rmal
Laboratory Parameter	Study Day		u	%	u	%		u	%	u	%		u	%	u	%
Any Parameter	Baseline		x	х.х	х	х.х		х	X.X	х	х.х		х	х.х	х	х.х
	Day 28 (Visit 03)															
	Day 42 (Visit 03B)															
	Day 56 (Visit 04)	·														
	Day 70 (Visit 04B)	·														
	Day 84 (Visit 05)															
	Day 112 (Visit 06)															
	Max Post Baseline															
[Parameter 1]	Baseline															
	Day 28 (Visit 03)															
	Day 42 (Visit 03B)															
	Day 56 (Visit 04)															
	Day 70 (Visit 04B)															
	Day 84 (Visit 05)															
	Day 112 (Visit 06)															

		670	- - -	injectio	SU	2 (EVI	5	i	injectio	SU-	1NA, 4	Crot	1p 3: 8	mg ZI injectio	N V WL	DNA
		Z	No	rmal	Abn	ormal	Z	No	rmal	Abn	ormal	Z	Nor	mal	Abne	ur me
Laboratory Parameter	Study Day		u	%	u	%		u	%	u	%		u	%	E	•`
	Max Post Baseline															
[Parameter 2]	Baseline															
	Day 28 (Visit 03)															
	Day 42 (Visit 03B)															
	Day 56 (Visit 04)															
	Day 70 (Visit 04B)															
	Day 84 (Visit 05)															
	Day 112 (Visit 06)															
	Max Post Baseline															

Distribution of Laboratory Results (Ordinal-Graded) by Parameter, Severity, Study Day, and Study Group – Part A, Group 1 Table 111:

[For graded parameters, in tox table]

			Norm	al	Grade	1	Grad	le 2	Grad	e 3	Grad	e 4
Laboratory Parameter	Study Day	Ν	n	%	n	%	u	%	u	%	n	%
Any Parameter	Baseline		х	х.х	х	х.х	х	х.х	х	х.х	х	х.х
	Day 28 (Visit 03)											

			Norn	ıal	Grade	e 1	Grad	le 2	Grad	e 3	Grad	e 4
Laboratory Parameter	Study Day	N	u	%	n	%	u	%	n	%	u	%
	Day 42 (Visit 03B)											
	Day 56 (Visit 04)											
	Day 70 (Visit 04B)											
	Day 84 (Visit 05)											
	Day 112 (Visit 06)											
	Max Post Baseline											
[Parameter 1]	Baseline											
	Day 28 (Visit 03)											
	Day 42 (Visit 03B)											
	Day 56 (Visit 04)											
	Day 70 (Visit 04B)											
	Day 84 (Visit 05)											
	Day 112 (Visit 06)											
	Max Post Baseline											
[Parameter 2]	Baseline											
	Day 28 (Visit 03)											
	Day 42 (Visit 03B)											
	Day 56 (Visit 04)											
	Day 70 (Visit 04B)											
	Day 84 (Visit 05)											
	Day 112 (Visit 06)											

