#### Criteria applicable to women and adolescents of childbearing potential:

- 19. Negative result on a human chorionic gonadotropin pregnancy test (urine or serum) on day of randomization before receiving study product
- 20. Agree to use effective means of birth control from at least 21 days before randomization through 12 weeks after the last product administration

Criteria applicable to adolescents:

- 21. Capability of the parent/guardian of the minor to understand and comply with planned study procedures.
- 22. Capability of the minor and their parent/guardian to provide assent/informed consent

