#### 8.6.3. Other Risks

Blood drawing may cause pain, bruising, fainting, and, rarely, infection at the site where the blood is taken.

We do not know the possible effects of the study vaccine on the fetus or nursing infant. Therefore, females of childbearing potential will be tested for pregnancy prior to each product administration.

It is possible that the standard medical tests performed as part of this research protocol will result in new diagnoses. Depending on the medical findings and consequences of being provided with the new medical information about health status, the study subject may view this aspect of study participation as either a risk or a benefit. Any such information will be shared and discussed with the subject and, if requested by the subject, will be forwarded to the subject's primary health care provider for further workup and management.

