# 8.5. Pregnancies

Female subjects of childbearing potential will receive pregnancy prevention counseling throughout the study. Women will be asked to notify the site immediately if they suspect or learn they are pregnant during this study. In case of pregnancy, subjects will be removed from the product administration schedule but may have limited clinic contacts and blood draws at the discretion of the site PI and IND Sponsor. The pregnancy outcomes are captured by the Pregnancy eCRF.

A table summarizing the total pregnancies, number of live births, miscarriages, elective abortions, ectopic pregnancies, still births, congenital anomalies, and neonatal deaths by treatment will be presented (Table 108 for Part A, Table 109 for Part B, Appendix 1). In addition, a listing of pregnancies and outcomes will be presented (Listing 40 for Part A and Listing 41 for Part B, Appendix 3).

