#### Listing 40: Pregnancy Reports, Part A

Treatment Group	Subject ID	Pregnancy Number	Date Site Notified	Start Date of Last Menstrual Period	Gravidity	Parity	Stated Method of Contraception	Date of Delivery or Pregnancy Termination	Estimated Gestational Age	Pregnancy Outcome	If live or still birth, Any Congenital Anomalies or Birth	If live birth, Neonatal Death?
											Defects?	
Comments:												
Comments:												

Listing with similar format:

Listing 41: Pregnancy Reports, Part B

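### The pregnancy tables count congenital anomalies only after live or still birth, which is narrower than the by-treatment count promised in SAP 8.5

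*Combined protocol and SAP*

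**What the plan says.** SAP 8.5 commits to "A table summarizing the total pregnancies, number of live births, miscarriages, elective abortions, ectopic pregnancies, still births, congenital anomalies, and neonatal deaths by treatment", in the tables titled "Number of Pregnancies by Outcome and Study Group" (Table 108 for Part A and Table 109 for Part B), with the individual reports in Listings 40 and 41. The sentence sets no condition on which outcomes may carry an anomaly. Outcomes come from the Pregnancy eCRF, which is not reproduced in the documents.

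In the Table 108 shell the row "Congenital anomalies" appears twice, once after the live birth row and once after the still birth row. Miscarriage, elective abortion and ectopic pregnancy are single rows with nothing beneath them. Table 109, "Number of Pregnancies by Outcome and Study Group – Part B", takes the same format. There is no row that totals anomalies over all pregnancies.

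The anomaly column of Listing 40 (Listing 41 follows it) opens with a condition: "If live or still birth, Any Congenital Anomalies or Birth" defects. The same listing also gives treatment group, last menstrual period date, pregnancy outcome and a comments line.

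Three parts of the protocol bear on this. Section 4.2.7 records every pregnancy that begins during the study and obliges the site to learn its outcome. Section 8.6.3 states: "We do not know the possible effects of the study vaccine on the fetus or nursing infant". Section 5.2.2 makes a congenital anomaly in a subject's offspring an SAE, reportable through the last study visit.

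**The concern.** The SAP text and the shell that implements it do not count the same thing. Under the shell, whether a known anomaly is counted depends on how the pregnancy ended, not on whether the anomaly was present.

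The item matters in this trial. Protocol 1.6 and 6.3.2 choose ages 15 to 35 in Part B for reproductive potential. Protocol 1.1 describes fetal harm as a causal consequence of Zika infection in pregnancy. The vaccine's effect on the fetus is stated to be unknown. Someone who reads the anomaly rows of Table 109 as the count announced in SAP 8.5 would take a partial count for a complete one.

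**Working it through.** No stated figure needs reproducing; this is a check of the shells against the text. The nesting is read from row order, and the condition in the Listing 40 column header supports that reading.

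| How the pregnancy ends | Own row in Tables 108–109 | Anomaly row after it | Anomaly column in Listings 40–41 |
|---|---|---|---|
| Live birth | yes | yes | applies |
| Still birth | yes | yes | applies |
| Miscarriage | yes | no | does not apply |
| Elective abortion | yes | no | does not apply |
| Ectopic pregnancy | yes | no | does not apply |

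**One case traced through.** Take a pregnancy in which a fetal anomaly is known.
- If it ends in live birth, it adds 1 to total pregnancies, 1 to live births and 1 to anomalies.
- If it ends in elective abortion, it adds 1 to total pregnancies, 1 to elective abortions and 0 to anomalies.

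SAP 8.5 read on its own would count the anomaly both times.

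**Direction and size.** Let A be the known anomalies in an arm and q the share of them in pregnancies that do not end in live or still birth. The table shows A × (1 − q). It cannot exceed A, and it falls short whenever q > 0. The documents give no value for q.

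**Effect on the comparison.** With v for vaccine and p for placebo, the ratio of tabulated counts is [A_v × (1 − q_v)] / [A_p × (1 − q_p)]. If q_v = q_p, this reduces to A_v / A_p. The absolute counts fall but the ratio does not move. Protocol 4.2.4.1 and 6.4.6 blind subjects and assessing staff in Part B, and nothing in the documents suggests that q differs by arm.

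**Does the SAE route recover the missing cases?** In part.
- The Protocol 5.2.2 criterion refers to offspring, which leaves a miscarried or terminated fetus unclear.
- SAE reporting stops at the last visit, while Protocol 4.2.7 still requires the outcome to be learned. In Part B, a pregnancy that ends g weeks after the last menstrual period ends after the last visit if that period began later than Week 96 − g. Assuming g = 40 for term (not a document figure), the cut-off is 96 − 40 = Week 56. Pregnancies that end early have smaller g, so their cut-off is later and fewer of them are affected, but not none.
- Table 98 counts subjects by MedDRA term, without a pregnancy denominator, and neither SAP 8.4 nor 8.5 describes a reconciliation with Tables 108 and 109.

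**The case against.** The strongest reply is that the information is not lost to the trial. An anomaly in offspring is an SAE, and Protocol 5.2.2 also lets a site investigator report any event judged serious. SAEs are tabulated by study group in Table 98, listed in Tables 99 to 101 and described in the Table 106 narratives. Listings 40 and 41 have an outcome field and a comments line where an anomaly could be written. Pregnancies that end early are also more likely than births to finish while SAE reporting is still open. All of this stands, and it limits the consequence. It does not make the pregnancy table match SAP 8.5, and it leaves the gaps set out above.

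A second reply is that the Pregnancy eCRF is not in the documents. It may already collect anomalies for every outcome, or it may collect none after an early loss. That stands too: the cost of the fix is not fully known, and a new row may hold incomplete data.

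A third reply is that pregnancy outcome is neither an objective in Protocol Section 3 nor a listed safety parameter in Protocol 6.2.1. This is correct and keeps the point modest. The SAP nevertheless chose to promise the count, and the shell should deliver it.

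**Conclusion.** The mismatch is real. Tables 108 and 109 and Listings 40 and 41 restrict anomalies to live and still births, while SAP 8.5 does not. The absolute anomaly count in each arm can be too low, by an unknown amount. This rests on reading SAP 8.5 as unrestricted, which is its plain wording, and on at least one anomaly being known in a pregnancy that ends another way. No primary or secondary analysis changes.

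Three stronger readings are tempting, and the documents do not support them.
- **A stated percentage of anomalies is missed.** Any figure put in for q comes straight back out as the loss, so it would restate an assumption and not measure anything.
- **The comparison between arms is biased.** This would need q to differ by arm, and no reason for that is given in a blinded Part B.
- **Pooling conceptions near to and remote from vaccination is an error.** Birth control is required "through 12 weeks after the last product administration", which on schedule ends at Week 8 + 12 = 20. That leaves 76 of 96 weeks (79%) of Part B follow-up and 12 of 32 weeks (37.5%) of Part A follow-up beyond it. These are shares of follow-up time, not of conceptions. The tables are descriptive counts with no planned ratio or test that could be diluted. No section promises a timing split, and the last menstrual period date is listed for each pregnancy. A split is optional.

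**What to change.** 1. In Tables 108 and 109, add a congenital/fetal anomaly row under elective abortion and under miscarriage.
2. Add a total row for any congenital anomaly, and reconcile it with the anomaly SAEs in Tables 98 to 100.
3. In Listings 40 and 41, make the anomaly column apply to any pregnancy outcome, with status reported as known, unknown or not assessed, so that a blank is not read as no anomaly.

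Make the change before database lock and unblinding, so that the added rows are not post hoc. The cost is a few table rows, a listing header and possibly one eCRF query. No extra visits or tests are needed. The downside is incomplete information after early losses, which the unknown and not-assessed categories make visible.
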